6. STUDY POPULATION

6.1 Study site

All enrollment and data collection activities will occur at the Thanh Hoa Provincial Centre of Reproductive Health.

6.2 Eligibility criteria

The study will enroll approximately 500 couples with roughly equal distribution to the two study arms. Couples must speak Vietnamese to be eligible for study participation.

In addition, women must meet all of the following criteria at enrollment to be eligible:

- Be 18-45 years of age;
- Not currently using a modern contraceptive method other than condoms or intending to start using a modern contraceptive method other than condoms in the next 6 months;
- Willing to use the assigned study condoms as the sole method of contraception for the next six months;
- Not breastfeeding;
- Not known to be pregnant;
- Want to avoid pregnancy for at least the next six months; **and**
- Be in a monogamous relationship for at least the past six months with her current male partner.

Couples are ineligible for study participation if either person in the couple is known to be HIV-positive or has any of the following contraindications to CSD500 use (see Package Insert):

- History of low blood pressure or heart condition;
- Current use of medication for anemia, blood pressure, erectile dysfunction (man only), migraines, headaches or glaucoma;
- Inflamed or broken skin that the condom could come into contact with (man only); **or**
- Latex allergy or sensitivity.

Both the woman and her male partner need to be willing and able to consent to the study procedures, including the use of the assigned study condoms.

Our justification for excluding women who are known to be pregnant or already using a modern method of contraception other than condoms and couples in which either partner has a known HIV-infection is that these individuals might differ in unknown ways from others with respect to

their adherence to the promotion of condoms for avoiding semen exposure. Furthermore, individuals who are known to be HIV-positive typically receive more intensive safer sex counseling, and the scientific integrity of the study findings require that all participants receive standardized condom counseling according to their study arm.

7. STUDY AIMS

The study has three main aims.

7.1 Aim 1: To evaluate whether CSD500 provided to improve sexual pleasure, as compared to the standard condom, results in less semen exposure among women in an established relationship

We hypothesize that providing women in an established relationship with CSD500 accompanied by counseling focusing on the new condom's ability to improve male performance will result in less unprotected vaginal sex than providing the standard condom with traditional counseling focusing on disease and pregnancy prevention only. The primary outcome is the relative risk (RR) comparing PSA positivity (per established threshold of >1 ng of PSA per mL vaginal swab eluate) at the 2, 4 and 6-month follow-up visits between the two study arms.

7.2 Aim 2: To evaluate the effects of CSD500 provision on men and women's reports of sexual pleasure compared to the standard condom

We will assess sexual pleasure with the Quality of Sexual Experience (QSE) scale, which is a validated measure of the pleasure and satisfaction of event-level sexual experiences (Sanders 2013). The construct of sexual pleasure can vary dramatically between individuals. For example, when interpreting a sexual act as pleasurable, individuals could be focused on different types of activity (e.g., foreplay, touch, use of erotica or toys, and oral or anal intercourse) or different aspects of the experience (e.g., orgasm or even pain). In order to account for the diversity of experiences that might make a sexual act pleasurable for an individual, the QSE scale does not capture specific physical or emotional aspects of the experience, but rather measures seven broad, event-level, bipolar items. Note that CSD500 could increase erection duration, which could (positively or negatively) influence the man's perception of the sexual pleasure of the act. Thus, we will also consider a modified QSE scale that adds an item to assess pleasure related to the act's duration.

The QSE scale was validated for men using three single-item questions that measured the individual's assessment of 1) the overall quality of the sexual act; 2) the act compared to the individual's typical act; and 3) the occurrence and quality of the respondent's orgasm during the act (Sanders 2013). QSE scores predicted much of the variance and were statistically significantly correlated ($P < 0.001$) with each of the measures. The scale also had high internal consistency (Cronbach's alpha of 0.96).

7.3 Aim 3: To identify correlates of semen exposure measured by PSA positivity

We hypothesize that condom usage will differ by demographic (e.g., age and marital status), personal (e.g., sexual relationship power), and study-related factors (e.g., length of follow up). To date, most evidence on correlates of condom nonuse is derived from studies where women were asked to report on their sex and condom use behavior; **consequently, these studies might have identified correlates of reporting unprotected sex rather than correlates of**

actual unprotected sex. No published research has used a semen biomarker to characterize women in an established relationship who engage in unprotected sex.

8. STUDY PROCEDURES

For an overview, see “Schedule of study procedures.”

8.1 Recruitment

Study staff will recruit women attending the Thanh Hoa Provincial Centre of Reproductive Health to the study using a standard Recruiting Script and the Study Brochure (see Attachments). Also, we will display the Study Poster (see Attachment) throughout the Thanh Hoa Provincial Centre of Reproductive Health. Initially, we will not recruit from outside of the Centre to ensure a slow rate of enrollment. Depending on the enrollment pace, we may start to recruit outside of the Centre. This recruitment will involve displaying the Study Poster and distributing the Study Brochures in places of employment (e.g., factories and school teachers) in Thanh Hoa city. This passive recruitment will require those interested in participating in the study to attend the Centre to obtain more information.

If their male partner is not present at the Centre, women will be asked to return with him to complete the enrollment visit.

Staff will complete the Eligibility Assessment Form to determine the couple’s eligibility. Women who are potentially interested in starting a modern contraceptive method other than condoms will be referred following standard care and will not undergo any further recruitment to the study.

8.2 Enrollment visit

If the couple is eligible per the Eligibility Assessment Form, study staff will conduct the consent process by reading the Annotated Enrollment Consent Form aloud to the couple in a private location and answering any questions. Only couples who demonstrate comprehension of the embedded questions during the consent process and who sign the Enrollment Consent Form will be enrolled.

The REDCap software program will provide the arm assignment after each couple is enrolled into the trial. Study staff will record the couple’s names, their unique participant identification numbers (PINs), and their assigned arm onto the Participant Identification Log. In the presence of the female participant only, staff will administer the Female Enrollment Questionnaire, and a study clinician will collect a double-headed vaginal swab per established procedures (Gallo 2013a). In the presence of the male participant only, staff will administer the Male Enrollment Questionnaire. Staff will provide the appropriate condom counseling (see Counseling Checklist: Control Arm and Counseling Checklist: Intervention Arm) to the couple together, and distribute the assigned study condoms. Participants in the intervention arm will receive the Futura Max Information Sheet. At the end of the enrollment visit, staff will administer the Participant Contact Form to the couple and will provide the male and female partner each with 110,000 VND (~5 USD) as compensation for their time for participation and travel costs to the clinic.

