2. STUDY SUMMARY

This randomized controlled trial will test whether promoting the novel condom CSD500 (Futura Medical Developments; Surrey, UK) for improved sexual pleasure results in couples having less unprotected vaginal sex – measured with a biological marker of recent semen exposure – compared to the promotion of a standard condom for disease and pregnancy prevention. CSD500 contains an erectogenic drug and was developed to improve sexual pleasure by increasing penile firmness, size, and erection duration.

We will recruit eligible, monogamous, heterosexual couples at Thanh Hoa Provincial Centre of Reproductive Health in Vietnam to participate in a randomized controlled trial (RCT) of two balanced arms of approximately 250 couples each. At enrollment and at three follow-up visits scheduled at 2, 4 and 6 months after enrollment, we will provide condom counseling, will collect double-headed vaginal swabs to test for the semen biomarker, prostate-specific antigen (PSA), and will administer a questionnaire to the female participants on their demographics, sexual and condom-related attitudes and practices, including sexual pleasure and perceptions of partner's sexual pleasure. Although the intervention is directed to the women, couples will be enrolled to ensure that the male partners consent to CSD500 use. After enrollment, male participants will not participate in study visit activities, including data collection, until the time of their female partner's final 6-month visit. Because of the differences in counseling messages, participants and study staff at the site cannot be blinded to arm assignment.

Primary aims:

1. To evaluate whether CSD500 provided to improve sexual pleasure, as compared to the standard condom, results in less semen exposure among women in an established relationship
2. To evaluate the effects of CSD500 provision on men and women's reports of sexual pleasure compared to the standard condom
3. To identify correlates of semen exposure measured by PSA positivity

Study design: RCT with two arms: CSD500 for sexual pleasure or the standard condom currently provided for pregnancy and disease prevention

Study site: Thanh Hoa Provincial Centre of Reproductive Health

Data collection: Women: questionnaires and vaginal swabs for PSA testing at enrollment and the 2, 4, and 6-month visits
Men: questionnaires at enrollment and the 6-month visit

Sample size: ~500 couples with balanced assignment to the two study arms

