9.2 Randomization

After having been determined to be eligible and having provided written consent for participation, couples will be randomized to one of the two study arms in roughly equal proportions. The Statistician will prepare the randomization program in REDCap before study initiation. The concealment of allocation process will be accomplished using the relevant function in the REDCap electronic data capture system.

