10. DATA MANAGEMENT

Given the potential for low participant literacy, trained study staff will administer all study forms and questionnaires and will electronically record responses directly onto a laptop computer using REDCap software. REDCap, which is supported by the Center for Clinical and Translational Science (CCTS) at OSU, facilitates the transmittal of secure, encrypted and password-protected data. CCTS will prepare the data entry screens with built-in quality control checks. Entered data will be instantaneously uploaded behind the secure OSU firewall. The PI will monitor the data during the study to resolve any potential issues upon detection.

In the case of internet outage or other technical difficulties, study staff will record data onto paper forms using a pen. These data will be entered into REDCap when the internet access is restored. PSA test results will be sent from the UNC laboratory to the PI in an electronic spreadsheet. The Site Investigator and PI will review the data files on an ongoing basis for accuracy. To maintain participant confidentiality, only a coded PIN will identify all data collection forms (DCFs), reports, and other records. Participants' names will be stored separately in a locked file in a locked office at the study site. No reports will link individual names with person-level data. Unique PINs will be used to link participant-specific data. All records will be secured in a locked room, accessible only by trained study staff. All computer entry and networking programs will be done with coded numbers only. Electronic files will be password-protected, with access only by authorized study personnel. Clinical information will not be released without written permission of the participant, except as necessary for monitoring by OSU or its designee.

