13.3 Description of risks

This study poses no more than minimal risk to participants. The active ingredient in CSD500 can cause headaches, faintness and nausea, loss of sensation, dizziness and skin irritation (see Package Insert). Participants will be instructed to stop using the study condoms if either they or their partner experience any of these symptoms and will be referred for standard care, as indicated.

Participants may experience psychological risks associated with answering questions about sensitive topics or reporting attitudes and behaviors, such as their sexual activity and details of their sexual relationships. Several measures have been implemented to minimize these risks. First, during the consent process, participants will be advised that they are free to decline study participation. Participants also will be informed that they can decline to answer any questions. Participants also will be informed of their freedom to terminate the interview or visit at any time. All interviews that take place in-person will occur in a private setting by interviewers who have been trained thoroughly on the importance of confidentiality, the procedures to protect a participant's confidentiality, and the penalties associated with breaches of confidentiality.

Participants' personal information will be kept confidential. Access to the signed consent forms and the Participant Identification Log (i.e., the roster linking participant names and PINs) will be limited to authorized study personnel and remained locked in a file cabinet when not in use.

We will not perform any genetic testing.

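### As section 8.2 is narrated, the arm can be released and logged before the staff-administered enrollment questionnaires; taking baseline first in the same visit is a minor, nearly free improvement

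*Combined protocol and SAP*

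**What the plan says.** Section 8.2 makes consent the enrolling event: only couples who show comprehension and "who sign the Enrollment Consent Form will be enrolled". Next, "The REDCap software program will provide the arm assignment after each couple is enrolled into the trial". Staff then record names, identification numbers "and their assigned arm onto the Participant Identification Log". After that, with the woman alone, "staff will administer the Female Enrollment Questionnaire, and a study clinician will collect a double-headed vaginal swab per established procedures"; the male questionnaire follows, and arm-specific counseling and condom distribution come last.

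Section 9.2 agrees with this. After eligibility and "having provided written consent for participation, couples will be randomized to one of the two study arms". Completed baseline data are not a condition.

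On who collects the data, section 10 says that "trained study staff will administer all study forms and questionnaires and will electronically record responses directly onto a laptop computer using REDCap software". On blinding, section 2 says: "Because of the differences in counseling messages, participants and study staff at the site cannot be blinded to arm assignment". Section 9.3.1 keeps the Statistician and the laboratory masked until the primary analyses are done.

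**The concern.** Read in the order given, site staff can hold the arm assignment while they take self-reported baseline answers. The stated reason for not blinding the site is the counseling, and no counseling has taken place at that point, so this exposure is avoidable.

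Three uses of enrollment data could be touched:

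- the descriptive baseline tables in section 9.3;
- self-reported Aim 3 covariates measured at enrollment. Perceived risk of infection or pregnancy, motivation to avoid these, and regulatory focus are the most exposed, because they lie close to what the two counseling messages contrast;
- the Aim 3 secondary outcome of self-reported unprotected sex in the past 48 hours, if it is asked at enrollment. The supplied text does not settle this.

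There is also a smaller point. Section 13.3 says: "Participants also will be informed of their freedom to terminate the interview or visit at any time". A couple who stop partway through baseline would, in the narrated order, already be randomized.

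**Working it through.** **Order of steps.** Sections 8.2 and 9.2 do not conflict. Section 9.2 sets an earliest time for randomization (eligible, consented), and section 8.2 places release of the arm after that time and before the questionnaires. Neither requires baseline first, and nothing in the text withholds the arm from interviewers. The Schedule lists the Randomization Assignment Form above both enrollment questionnaires, but it is weak evidence of timing. It also lists assignment of the identification number above eligibility and consent, and counseling and condoms above the swab, whereas section 8.2 has the swab before counseling.

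**Size.** The plan gives no figure for interviewer influence, so there is none to reproduce. The following is a linear approximation.

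Inputs:
- Arms 1:1, so the variance of the arm indicator is 0.25 (section 9.2).
- Follow-up PSA positivity of 15% in control and 9% or 7.5% in intervention (section 9.1).
- A self-reported covariate with SD 1 and a constant shift d in one arm. **Assumption:** d = 0.10 to 0.25.

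1. *Baseline table.* The spurious between-arm difference is d itself, 0.10 to 0.25 SD.

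2. *Aim 3, enrollment PSA.* It reflects exposure before the visit and is assayed by a masked laboratory, so it is independent of arm. The shift only adds variance: Var = 1 + d²/4. The slope is multiplied by 1/(1 + d²/4).
   - d = 0.10: 1/1.0025 = 0.9975, an attenuation of 0.25%.
   - d = 0.25: 1/1.015625 = 0.9846, an attenuation of 1.5%.

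3. *Aim 3, follow-up PSA, arm left out of the model.* Absolute spurious slope = d × 0.25 × (0.15 − p_int)/(1 + d²/4).
   - p_int = 0.09, d = 0.10: 0.10 × 0.25 × 0.06/1.0025 = 0.00150, or 0.150 points per SD.
   - p_int = 0.09, d = 0.25: 0.25 × 0.25 × 0.06/1.015625 = 0.00369, or 0.369 points.
   - p_int = 0.075, d = 0.10: 0.10 × 0.25 × 0.075/1.0025 = 0.00187, or 0.187 points.
   - p_int = 0.075, d = 0.25: 0.25 × 0.25 × 0.075/1.015625 = 0.00462, or 0.462 points.

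4. *Arm included.* A constant shift is absorbed by the arm term, so there is no attenuation and the spurious slope is zero. A simulation of 4 million records at p_int = 0.09 agreed: attenuation ratios of 0.998 and 0.985 and slopes of 0.146 and 0.366 points without arm; 1.000 and 0 with arm. The covariates listed in section 9.3.3 do not include arm, while section 7.3 speaks of study-related factors, so both cases are shown.

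5. *Against sampling error.* Section 9.1 assumes 10% never return (500 × 0.9 = 450 women), rho = 0.23, and a missed-visit rate that can be read as 3 × 0.75 = 2.25 or 3 − 0.25 = 2.75 visits per woman. Effective observations are about 450 × m/(1 + (m − 1) × 0.23): 450 × 2.75/1.4025 = 882, or 450 × 2.25/1.2875 = 786.
   - Mean positivity 12% (15% and 9%): SE = √(0.12 × 0.88/882) = 1.09 points, or 1.16 with 786.
   - Mean positivity 11.25% (15% and 7.5%): SE = √(0.1125 × 0.8875/882) = 1.06 points, or 1.13 with 786.
   - The spurious slope is thus between 0.150/1.16 = 0.13 and 0.462/1.06 = 0.44 of one standard error.

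6. *Self-reported 48-hour exposure, if asked at enrollment.* An arm-related shift δ in the probability of reporting would appear as a between-arm difference of δ. If a covariate were shifted as well, the formula in step 3 applies with δ in place of (0.15 − p_int). The documents give no basis for δ, so no number is offered.

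Reordering the steps changes no input to section 9.1; the planned 500 couples and the power are unaffected.

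**The case against.** The strongest reply is that nothing here is an error. The two sections agree, a site may already take baseline first, and the documents do not say that the person who logs the arm is the interviewer or that couples know their arm before counseling. The enrollment questionnaires and the Randomization Assignment Form are attachments outside the supplied text, so their content and any timing instructions cannot be checked. Many Aim 3 items (age, age difference, past partners, contraceptive history) are factual and unlikely to move. Even with an assumed d, the bias is under half a standard error and is removed by including arm. Site staff remain unblinded at follow-up, so any correlate asked again then is still taken by staff who may know the arm. All of this stands, and it is why the point is minor. It does not remove the point: the exposure at baseline is avoidable, and the plan leaves it to local practice.

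A reader might go further and infer that the narrated order biases the primary result or breaks allocation concealment. The documents do not support that. Assignment follows eligibility and consent and uses the REDCap concealment function. Aim 1 rests on follow-up PSA from a masked laboratory, and section 9.3.1 names no baseline covariate. The Aim 2 between-arm comparisons use follow-up scores. Nor does the Schedule's row order show that the arm is known first, for the reason given in the check.

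**Conclusion.** A minor design improvement, not a flaw in the primary analysis. The text allows the arm to be released and logged before self-reported baseline data are taken, and it neither requires nor forbids the safer order. What could be affected is the baseline tables, self-reported Aim 3 covariates taken at enrollment, and the self-reported 48-hour outcome if it is asked then. The likely size is small: at most about 1.5% attenuation, or 0.46 points per SD with arm omitted. These sizes rest on an assumed constant shift of 0.10 to 0.25 SD and on interviewers knowing the arm, neither of which the documents state. A shift that varied with the respondent's characteristics would not be fully removed by including arm. The number of couples who might stop during baseline cannot be estimated from the documents.

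**What to change.** - **Section 8.2:** complete both enrollment questionnaires and the vaginal swab first. REDCap then releases the arm and staff log it, immediately before counseling and condom distribution. Names and identification numbers can still be logged at consent; only the arm entry waits.
- **Section 9.2:** make randomization follow eligibility, consent and the baseline session, so that couples who stop during baseline are not randomized. State that declining single questions, which section 13.3 permits, does not block randomization.
- **Schedule of study procedures:** move the Randomization Assignment Form row below the enrollment questionnaires and the swab, to match.

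The cost is a change of order within the same visit, a separate later entry of the arm on the log, and small text edits in three places. It needs no extra visit, staff or data item, and no change to sample size.
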